**Is this a multi-site study (i.e. Each site has their own Principal Investigator)?**

No

**Does this protocol involve the use of animals?**

Yes  No

## **4.0 Project Information**

### **4.1 \* Has another IRB/HRPP reviewed this study or will another IRB/HRPP be reviewing this study? If Yes, answer the questions according to the IRB/HRPP Determination.**

Yes  No

IRB Name	Review Date	Determination
No records have been added		

### **4.2 \* Is this a research study or a Compassionate Use/Emergency Use/HUD project?**

Yes  No

#### 4.3 What type of research is this?

- Biomedical Research
- Clinical trial (FDA regulated)
- Behavioral Research
- Educational Research
- Psychosocial Research
- Oral History
- Other

#### 4.4 Are you conducting this project in pursuit of a personal degree?

Yes  No

#### 4.6 \* Is this human subjects research? (As defined by 32 CFR 219)

**Human subject means a living individual about whom an investigator (whether professional or student) conducting research:**

- (i) Obtains information or biospecimens through intervention or interaction with the individual, and uses, studies, or analyzes the information or biospecimens; or
- (ii) Obtains, uses, studies, analyzes or generates identifiable private information or identifiable biospecimens.

Yes  No

#### 4.7 \* Do you believe this human subjects research is exempt from IRB review?

Yes  No

## 5.2

### Will you have a Research Monitor for this study?

- Yes
- No
- N/A

## 6.0

### Data/Specimens

#### 6.1 Does the study involve the use of existing data or specimens only (no interaction with human subjects)?

- Yes
- No

## 7.0

### Funding and Disclosures

#### 7.1 Source of Funding:

Funding Source	Funding Type	Amount	
: Other Air Force Medical Support Agency	: Research Development : Testing and Evaluation (RDT&E) funds	595000	

Total amount of funding:

595000

#### 7.2 Do you or any other Investigator(s) have a disclosure of a personal interest or financial nature significant with sponsor(s), product(s), instrument(s) and/or company(ies) involved in this study?

- Yes
- No

If Yes, complete and attach Conflict of Interest forms for all key personnel

## 8.0

### Study Locations

#### 8.1 Is this a collaborative or multi-site study? (e.g., are there any other institutions involved?)

- Yes
- No

### 8.3 Are there international sites?

Attach international approval documents, if applicable, when prompted. Note: Ensure local research context has been considered

Yes  No

### 8.4 Is this an OCONUS (Outside Continental United States) study?

Yes  No

Select the area of responsibility:

Have you obtained permission from that area of responsibility? (This is a requirement prior to study approval)

Yes  No

## 9.0 Study Details

### 9.1 Key Words:

Provide up to 5 key words that identify the broad topic(s) of your study

Family Medicine Residency, Family Medicine

### 9.2 Background and Significance:

Include a literature review that describes in detail the rationale for conducting the study. Include descriptions of any preliminary studies and findings that led to the development of the protocol. The background section should clearly support the choice of study variables and explain the basis for the research questions and/or study hypotheses. This section establishes the relevance of the study and explains the applicability of its findings

Diastasis rectus abdominus (DRA) is a common finding among pregnant and postpartum women (3,6). A small number of studies have shown a correlation between DRA and reduced abdominal wall functioning and poor overall body image (5, 6); some studies have shown DRA to be associated with lumbopelvic pain (3). A study evaluating natural recovery of DRA after pregnancy showed some improvement in DRA and abdominal wall function compared to baseline, but did not return to baseline levels (6). DRA-specific exercise protocols have not been consistently effective in improving associated lumbopelvic pain and it is

unclear if abdominal functionality is improved (1, 2, 6). Ultrasound can be used to noninvasively and accurately measure DRA (3, 4, 5, 7). With general therapy, microcurrent treatments have been shown to improve muscle function and may reduce pain associated with muscular dysfunction, however no studies that we are aware of are using microcurrent to treat DRA. We wish to determine if frequency specific microcurrent treatment is an effective treatment for DRA. Secondarily we will assess lumbar and/or pelvic pain levels, urogynecologic symptoms, and overall body image after having microcurrent therapy. The significance of improving DRA in the postpartum military population may be that the service member can return to exercise sooner without pain and have improved strength, thereby allowing her to return to duty and meet military fitness standards

### **9.3**

#### **Objectives/Specific Aims/Research Questions:**

Describe the purpose and objective(s) of the study, specific aims, and/or research questions/hypotheses

Determine if frequency specific microcurrent therapy improves pain management of DRA by 30% or greater

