### **9.6 Benefit to the DoD:**

State how this study will impact or be of benefit to the Department of Defense

Improving pain management of DRA after microcurrent therapy in post-partum females may allow a faster, more effective return to activity, the return-to-duty transition and establishing personal readiness by meeting military fitness standards

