**Visit 1 (may be the same day as screening visit):**

- We will apply ultrasound gel and measure inter-rectus distance (IRD), 2 cm above and 2 cm below the umbilical ring, via ultrasound or if unable via ultrasound, via palpation and measuring tape.

-Begin treatment according to randomization group, patients will be instructed to leave microcurrent in place until treatment is over. Subjects will return to the clinic the day after visit 1 so that Research personnel can retrieve the microcurrent box. We will apply ultrasound gel and measure inter-rectus distance (IRD), 2 cm above and 2 cm below the umbilical ring, via ultrasound or palpation with tape measure (measurement will be the same technique as the original measurement).

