**Visit 3/week 4-12 (between week 4 and 12):**

- We will apply ultrasound gel and measure inter-rectus distance (IRD), 2 cm above and 2 cm below the umbilical ring, via ultrasound or palpation with tape measure (measurement will be same technique as original measurement)

-Administer Body Image States Scale (BISS) (5 minutes)

-Administer Pelvic Floor Impact Questionnaire- short form 7 (PFIQ-7) (5 minutes)

-Obtain Defense and Veterans Pain Rating Scale for lumbar pain and pelvic pain (DVPRS) (5 minutes)

Microcurrent Device: We will be using the Inspirstar microcurrent stimulator TENS device. It is an FDA 510k approved portable hand-held device used for the symptomatic relief of chronic pain. It generates low current intensity pulses in the ranges of 20 $\mu$ A to 400 $\mu$ A. For this study, we will use a treatment range of 100-300 $\mu$ A.

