**11.0****Statistical/Data Analysis Plan****11.1 Statistical Considerations:**

List the statistical methods to be used to address the primary and secondary objectives, specific aims, and/or research hypotheses. Explain how missing data and outliers will be handled in the analysis. The analysis plan should be consistent with the study objectives. Include any sub-group analyses (e.g., gender or age group). Specify statistical methods and variables for each analysis. Describe how confounding variables will be controlled in the data analysis

The primary outcome measures are inter-rectus distances (IRD) taken 2 cm above and 2 cm below the umbilical ring. Secondary outcome measures taken once at the final postpartum visit between weeks 4 and 12 are Body Image States Scale (BISS); Pelvic Floor Impact Questionnaire- short form 7 (PFIQ-7); and Defense and Veterans Pain Rating Scale for lumbar pain and pelvic pain (DVPRS). Employing these outcome measures, the statistical null hypotheses are as follows:

- H01 — there are no differences in IRD means between times, locations and treatment groups
- H02 — there are no differences in BISS means between treatment groups
- H03 — there are no differences in PFIQ-7 means between treatment groups
- H04 — there are no differences in DVPRS means between treatment groups

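### The only objective in section 9.3 is a 30% improvement in pain management, but the trial is designed, sized and tested on inter-rectus distance

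*Combined protocol and SAP*

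**What the plan says.** Pain is the stated aim in two places. Section 9.3 has a single objective, "Determine if frequency specific microcurrent therapy improves pain management of DRA by 30% or greater". Section 9.6 opens the benefit statement with "Improving pain management of DRA after microcurrent therapy in post-partum females". Section 12.5 also requires DRA pain for entry.

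The other sections put IRD first:

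- Section 9.2: "We wish to determine if frequency specific microcurrent treatment is an effective treatment for DRA", followed by "Secondarily we will assess lumbar and/or pelvic pain levels, urogynecologic symptoms, and overall body image after having microcurrent therapy".
- Section 11.1: "The primary outcome measures are inter-rectus distances (IRD) taken 2 cm above and 2 cm below the umbilical ring". H01 concerns IRD means. The pain scale, DVPRS, appears under H04 among the "Secondary outcome measures taken once at the final postpartum visit between weeks 4 and 12".
- Section 11.5: the 30% is a difference in IRD between the arms, and every mean, SD and detectable change in the power calculation is an IRD figure.
- Section 11.6: H01 is tested by repeated measures ANOVA; H02 to H04 by a two-sample t-test or Mann-Whitney U test.

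In section 10.1, DVPRS is listed at Visit 3 only. The lists for the screening visit, Visit 1 and Visit 2 contain no pain score. Section 10.2 names pain among the assessments but gives no time for it.

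**The concern.** The objective tells a reader what a positive trial would show. Here it names pain, and the confirmatory test concerns the width of a muscle gap. If H01 is rejected, the trial has shown an IRD difference and nothing about pain. If H01 is not rejected, the pain objective is not refuted either. Because the same 30% is attached to pain in 9.3 and to IRD in 11.5, either result could later be presented as the answer to the stated objective. That choice should be fixed while the assignments are still blinded.

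There is a second, lesser matter. Women enter with DRA pain, but its starting level is never scored. The plan therefore cannot describe change in pain, and it gives up the precision that a baseline score would bring.

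**Working it through.** **1. What the 30% refers to**

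| Section | Quantity | Role |
|---|---|---|
| 9.3 | Pain management, 30% or more | Only objective |
| 9.6 | Pain management | Benefit |
| 9.2 | Treatment of DRA; pain second | Rationale |
| 11.1 | IRD; DVPRS secondary | Primary outcome, H01 |
| 11.5 | IRD, 30% between arms | Sample size |
| 11.6 | IRD | Main model |

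Section 11.5 describes its detectable changes as smaller than the research objective but close to it. Dividing each by its mean gives:

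- 0.45/1.97 = 22.8%
- 0.47/2.39 = 19.7%
- 0.55/1.99 = 27.6%
- 0.36/1.30 = 27.7%

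These sit just below 30%, so section 11.5 is working with a 30% objective for IRD.

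**2. The plan's own power figure**

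Inputs from 11.5: N = 98, m = 3 repeated measures, alpha = 0.05, and the fourth location, which has the smallest standardised effect, d = 0.36/0.77 = 0.468, so f = d/2 = 0.234. The within-subject correlation rho is not stated; 0.5 is assumed.

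- lambda = N f² m / [1 + (m − 1) rho] = 98 × 0.2338² × 3 / 2 = 8.03, on 1 and 96 degrees of freedom.
- Power = 0.801, the stated value. At rho = 0.3 it is 0.880; at rho = 0.7 it is 0.726.

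No pain quantity enters. This shows what the number was built from. It does not show that the sample size is adequate (see the objection).

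**3. What a baseline DVPRS would add**

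Inputs: 98 planned completers (11.2), so 49 per arm at 1:1; two-sided alpha 0.05; power 80%. The documents give no baseline correlation, so r is assumed. ANCOVA multiplies the error variance by 1 − r². Detectable d comes from the noncentral F with lambda = (49/2) d² / (1 − r²), on 96 degrees of freedom without a baseline and 95 with one. The 95% CI half-width in SD units is t(0.975) × √(2/49) × √(1 − r²).

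| | Visit 3 only | r = 0.3 | r = 0.5 | r = 0.7 |
|---|---|---|---|---|
| 1 − r² | 1 | 0.91 | 0.75 | 0.51 |
| Detectable d | 0.57 | 0.55 | 0.50 | 0.41 |
| CI half-width (SD) | 0.40 | 0.38 | 0.35 | 0.29 |
| Equivalent Visit 3-only completers per arm, 49/(1 − r²) | 49 | 54 | 65 | 96 |

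**The case against.** The strongest reply is that the defect is confined to the wording of the aims. Section 11 is consistent about IRD, and an analyst following it would know which endpoint is primary. That is right, and it limits the severity: the H01 analysis does not change. But the objective is what a reader will hold the result against, and 9.3 states no other.

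A second reply is that 9.3 may express the real intent, since 9.6 and the entry criterion are also about pain, and the objective mentioned in 11.5 may be only that section's own earlier sentence. This stands in part. The documents favour IRD as primary but do not prove the sponsor's intent. If pain were meant to be primary, it would need a baseline score, a defined 30% criterion and its own power calculation.

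Three stronger readings are tempting and are not supported:

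- *That the pain comparison is invalid without a baseline.* It is not. A randomised comparison of Visit 3 scores is unbiased; what is lost is precision and a description of change.
- *That H04 is defective because it carries no 30% criterion.* H01 carries none either. Both are ordinary hypotheses of no difference, and a secondary pain outcome needs no such threshold.
- *That the IRD sample size is confirmed because 0.801 reproduces.* It reproduces only with the unstated rho of 0.5. Section 11.5 counts three repeated measures, while section 10.1 schedules four IRD measurements (before treatment, the next day, Visit 2 and Visit 3) and does not say which three are meant. If one of the three precedes treatment, the average between-group effect shrinks by a third. Then f = 0.468/3 = 0.156, lambda = 98 × 0.156² × 3 / 2 = 3.57 (unrounded f), and power is about 0.46. If all three follow treatment, 0.801 stands under rho = 0.5. The documents do not settle this, so the sample size is neither cleared nor faulted here.

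**Conclusion.** The contradiction is real and rests on the text alone: the sole objective in 9.3, echoed in 9.6, is not the quantity that 11.1, 11.5 and 11.6 make primary, size and test. It should be fixed, and confidence in this part is high. The primary IRD analysis is not invalidated; what fails is the link between its result and the stated objective.

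The missing baseline DVPRS is an opportunity for improvement and not an error. Its value depends on a correlation that the documents do not give. It ranges from slight (detectable d 0.57 to 0.55 at r = 0.3) to substantial (0.41 at r = 0.7), assuming 49 completers per arm and roughly normal scores.

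**What to change.** 1. Before unblinding, reconcile 9.3 and 9.6 with 11.1, 11.5 and 11.6. The reading best supported by the documents is a primary objective of a between-group IRD difference, with the 30% target as in 11.5, and DVPRS pain as secondary. This costs a wording amendment.
2. As an optional improvement, record DVPRS for lumbar and pelvic pain at Visit 1, before the device is applied. Analyse each Visit 3 score by ANCOVA on its own baseline and report the difference with a 95% CI. If the scores are non-normal, use a baseline-adjusted rank analysis (rank ANCOVA); an unadjusted Mann-Whitney test would discard the precision that the baseline was collected to gain.
3. State whether the lumbar and pelvic scores form one test or two, since H04 names a single DVPRS mean.

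Items 2 and 3 need about 5 minutes per woman, by the plan's own figure for DVPRS, at a visit already held, plus an analysis amendment. They need no new visit and no extra participants. A baseline can be obtained only from women not yet treated when the amendment takes effect.

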### **9.4 Study Design:**

Describe study design in one to two sentences (e.g., prospective, use of existing records/data /specimens, observational, cross-sectional, interventional, randomized, placebo-controlled, cohort, etc.). Specify the phase – Phase I, II, III, or IV – for FDA-regulated investigational drug research

Active duty or DoD beneficiary post-partum females aged 18 years or older who have met inclusion /exclusion criteria and are willing to participate in a randomized double-blind study assessing a microcurrent therapy treatment vs placebo (a microcurrent faux (fake) treatment) over a 12-week period post-partum. They will be recruited from the post-partum unit at 99MDG (see section 13.1).

### **9.5 Target Population:**

Describe the population to whom the study findings will be generalized

Active duty or DoD beneficiary females aged 18 years or older who are postpartum from a singleton gestation status post vaginal, who meet the inclusion and exclusion criteria will be recruited. No special populations (i.e. pregnant women, children, military basic trainees, prisoners, detainees) will be recruited.

### **9.6 Benefit to the DoD:**

State how this study will impact or be of benefit to the Department of Defense

Improving pain management of DRA after microcurrent therapy in post-partum females may allow a faster, more effective return to activity, the return-to-duty transition and establishing personal readiness by meeting military fitness standards

## **10.0**

### **Study Procedures, Data Management, and Privacy**

#### **10.1 Study Procedures:**

Describe step-by-step how the study will be conducted from beginning to end

Female Active duty members or DoD beneficiaries, aged 18 years or older, meeting the inclusion /exclusion criteria will be offered an opportunity to participate. They will be recruited from the postpartum unit at 99MDG (see Protocol Section 13.1). All of the below items are research-related unless marked as 'standard of care':

**Pre-Eligibility review:** Subjects who responded to advertisements or have given their permission to be contacted will be approached by a study staff member to discuss the subject's interest in the research study and to receive a pre-eligibility screening for study participation. The attached "Pre-Eligibility Review Script" will be used and response will be recorded. If the subject is interested in participating in the study, the study staff member will schedule a screening visit while the subject waits on the phone or in-person, in order to confirm the schedule appointment with the subject. Following the pre-screening procedure, the script will be shredded.

**Screening visit (within 3 months postpartum):**

- Obtain and document signed Informed Consent and HIPAA authorization.
- Review past medical and pregnancy history to verify inclusion and exclusion criteria.
- Collect demographic information to include age, weight (pounds), height (inches), BMI, DoD ID#, current email address (for scheduling), phone number, race, ethnicity.

**Randomization:** Subjects will be randomized into one of two research treatment groups with approximately 58 subjects in each arm:

- Group 1: Sham (fake) microcurrent therapy (placing the microcurrent pads on the patient and turning the microcurrent box on placebo mode ), for one treatment lasting a total of 7 hours and 10 minutes the device will worn at home and returned.
- Group 2: Frequency specific microcurrent therapy (100-300 $\mu$ A microcurrent amps) with Diastasis Recti Repair protocol (8), for one treatment lasting a total of 7 hours and 10 minutes the device will be worn at home and returned.

**Blinding:** [name] will be responsible for managing the excel spreadsheet that randomly assigns the patient to Group 1 or Group 2. She will place the randomization code into a sealed envelope and deliver it to the Research Technicians who will program the microcurrent boxes to either Group 1 (Sham microcurrent therapy) or Group 2 (microcurrent therapy). The blinded microcurrent boxes will be provided to the study staff to apply the microcurrent treatment. The remaining study staff will be blinded to the study treatment. If at any time a patient experiences an adverse event that requires breaking of the blind, [name] can provide the randomization assignment. At the conclusion of the study, and once all the subjects have completed treatment and follow up, [name] will provide the randomization assignments to the study staff to be included in the data analysis.

**Visit 1 (may be the same day as screening visit):**

- We will apply ultrasound gel and measure inter-rectus distance (IRD), 2 cm above and 2 cm below the umbilical ring, via ultrasound or if unable via ultrasound, via palpation and measuring tape.

-Begin treatment according to randomization group, patients will be instructed to leave microcurrent in place until treatment is over. Subjects will return to the clinic the day after visit 1 so that Research personnel can retrieve the microcurrent box. We will apply ultrasound gel and measure inter-rectus distance (IRD), 2 cm above and 2 cm below the umbilical ring, via ultrasound or palpation with tape measure (measurement will be the same technique as the original measurement).

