### **13.6 Withdrawal from Study Participation:**

Explain the process for withdrawal and specify whether or not the subjects will be given the opportunity to withdraw their data or specimens in the event they wish to withdraw from the study

If a participant first agrees to participate and then changes their mind, they are free to withdraw consent and discontinue participation at any time. Their decision will not affect their ability to receive medical care and will not be penalized or lose any benefits to which they would otherwise be entitled. There are no risks from withdrawing. They will be advised in the Informed Consent process that if they decide to withdraw from the study early, we will ask them to discuss their decision with the study staff. The researcher may withdraw them from the study prior to the study's end without their consent for one or more of the following reasons: Failure to follow the instructions of the researchers and study staff. The researcher decides that continuing their participation is not in their best interests. The study is cancelled. Other administrative reasons. Unanticipated circumstances. They become Pregnant. If they lose their status as a military health care beneficiary, they can no longer be included in the study.

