##### **Less Likely and Not Serious:**

##### **Ultrasound:**

- Skin sensitivity or allergic reaction to gel
- Discomfort with ultrasound exam

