##### **Microcurrent:**

- Discomfort with microcurrent treatment
- Skin sensitivity after treatment
- Skin damage
- Conditions may worsen
- Nausea

-If the device malfunctions, it could give an inadvertent electrical shock similar to a mosquito bite

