#### **14.2**

##### **Measures to Minimize Risks of Harm (Precautions, safeguards):**

For each research procedure or intervention, describe all measures to minimize and/or eliminate risk of harms to subjects and study personnel

Safeguards are in place for protecting subjects and their health data. The research consents and HIPAA Authorization Documents will be stored in a locked cabinet in a locked room. Safeguards are in place for protecting subjects. Risks related to the microcurrent will be minimized by proper use of the microcurrent device. Proper use includes software and firmware updates, cleaning pads after each patient, and daily inspection of cables. Subjects do not have to participate or answer any question that they do not want to

complete. If at any time the patient reports a side effect, they will be referred to one of the Investigators for care.

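### Adverse effects, wear time and early removal in the home session are not systematically asked about, recorded or compared by arm, and the wear instruction is not reconciled with sections 13.6 and 14.1

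*Combined protocol and SAP*

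**What the plan says.** Section 10.1 describes the active intervention as "for one treatment lasting a total of 7 hours and 10 minutes the device will be worn at home and returned", and the sham session has the same length and setting. Under Visit 1, "patients will be instructed to leave microcurrent in place until treatment is over". The next contact is described this way: "Subjects will return to the clinic the day after visit 1 so that Research personnel can retrieve the microcurrent box". Inter-rectus distance (IRD) is measured again then. Visit 2 lists IRD only. Visit 3 lists IRD, BISS, PFIQ-7 and DVPRS.

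Section 14.1 names five effects of microcurrent: discomfort, skin sensitivity, skin damage, worsening of conditions and nausea. It adds a sixth item: "If the device malfunctions, it could give an inadvertent electrical shock similar to a mosquito bite". All of these stand under the label "Less Likely and Not Serious".

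Section 13.6 says of participants that "they are free to withdraw consent and discontinue participation at any time". Among the grounds on which the researcher may remove a woman, it also lists "Failure to follow the instructions of the researchers and study staff".

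On handling harms, 14.2 says: "If at any time the patient reports a side effect, they will be referred to one of the Investigators for care". The blinding paragraph in 10.1 allows the code to be broken for an adverse event. Section 16.1 answers its prompt with one sentence that defers to IRB policy.

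**The concern.** There are two separate gaps.

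The first is measurement. If no scheduled contact asks about harm, what is recorded depends on which women choose to speak up. Counts will then be incomplete by an unknown amount, and possibly by a different amount in each arm. A low or zero count in the active arm could not be read as good tolerability. This has some weight because 9.2 says the authors know of no study using microcurrent for this condition, and 14.1 concedes that there may be unknown risks. A randomised sham arm is well suited to answering the question, but only if both arms are asked the same thing.

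The second is what happens to a woman who takes the device off before the session ends. The instruction states no exception, the protocol lists effects that could prompt removal, and 13.6 deals only with leaving the study. Without a stated rule, early removal could be handled as non-compliance, as withdrawal or as nothing at all, and it would leave no trace in the data.

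**Working it through.** **Reading the sections side by side.** The plan gives no figure on harms or wear time to reproduce. The power of 0.801 in 11.5 concerns IRD, and this point does not depend on it.

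| Place | Listed content | Adverse-effect question | Wear time or early removal |
|---|---|---|---|
| 10.1, next-day contact | box retrieval, IRD | none | none |
| 10.1, Visit 2 | IRD | none | none |
| 10.1, Visit 3 | IRD, BISS, PFIQ-7, DVPRS | none | none |
| 10.2, data list | demographics, history, pain, body image, strength, urogynecologic symptoms | none | none |
| 11.1 and 11.6 | H01 to H04 (IRD, BISS, PFIQ-7, DVPRS) | no harm outcome or analysis | none |
| 14.2 | staff care of the device; referral to an investigator | only once the woman reports | none |
| 16.1 | IRB policy | only once an event is known | none |

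The prompt in 16.1 asks how unexpected events will be identified, who reports them, how often they are reviewed and which severity scale applies. The one-sentence answer states none of these.

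**The wear instruction.** Section 10.1 tells the woman to keep the device on for 7 × 60 + 10 = 430 minutes. Section 14.1 lists effects that may occur in that time. Section 13.6 covers leaving the study at her wish, and removal by the researcher for not following instructions. None of the three addresses a woman who takes the device off early and wishes to stay in follow-up. The plan enrols 116 and expects 98 to complete, an allowance of 116 − 98 = 18. It does not say whether such a woman counts among the 18.

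**Illustration of what passive capture costs.** Inputs: n = 58 per arm (10.1, 11.4), or 98/2 = 49 completers per arm (11.2). The true rate p and the captured share c are assumptions; the documents give neither. The chance of recording at least one event in an arm is 1 − (1 − p·c)^n.

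| n | p | c = 1 | c = 0.5 | c = 0.25 |
|---|---|---|---|---|
| 58 | 2% | 69% | 44% | 25% |
| 58 | 5% | 95% | 77% | 52% |
| 58 | 10% | 99.8% | 95% | 77% |
| 49 | 5% | 92% | 71% | 46% |

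For example, with n = 58, p = 0.05 and c = 0.5: 1 − 0.975^58 = 0.770.

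If no events are recorded and every event would have been, the one-sided 95% upper bound on the true rate is 1 − 0.05^(1/58) = 5.0%, or 1 − 0.05^(1/49) = 5.9% with 49 women. With captured share c, the bound applies to p·c, so the bound on p is 5.03%/c: 10.1% at c = 0.5 and 20.1% at c = 0.25. With c unknown, no bound on p can be stated.

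**The case against.** **No contradiction.** A reader might infer that the wear instruction contradicts the right to stop. The documents do not support that. The instruction is an ordinary adherence instruction for one session, 13.6 is about leaving the study, and nothing visible forbids taking the device off. Section 14.2 adds that women need not take part in anything they do not want to. This objection stands: the sections are unreconciled, not contradictory.

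**Harms are not wholly unseen.** A reader might also infer that tolerability escapes notice altogether. It does not. Staff see each woman the next day, reported side effects go to an investigator, the blind can be broken for an adverse event, and IRB reporting applies. Worsening is partly covered by IRD at every contact and by DVPRS and PFIQ-7 at Visit 3, although those questionnaires are taken once, with no pre-treatment value. This stands too. What remains is that these routes do not ask about the other listed effects.

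**The risks are graded low.** Section 14.1 calls them minimal and not serious, limits shock to malfunction, and describes it as mild. The device is lawfully marketed under a 510(k). This limits the weight of the point.

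**Some absence cannot be checked.** The consent form was not available for this review, and the text shows no selection for the research monitor (5.2) or the monitoring plan (15.1). Wording on removal or reporting may exist there. It would not put an item into the visit lists or the data list, or an analysis into 11.6.

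**No tolerability aim is stated.** True: the objective and hypotheses concern pain, IRD and the questionnaires. The point is therefore an inexpensive improvement, not a failure to analyse a declared outcome.

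**Conclusion.** The concern holds in a limited form. In the visible text, adverse effects of the home session are not systematically elicited, recorded or compared by arm, and neither wear time nor early removal is captured. Separately, 10.1, 13.6 and 14.1 leave early removal with continued follow-up unaddressed.

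The documents do not fix the size of the loss, because the captured share is unknown. Under an assumed 5% true rate, the chance of recording any event among 58 women is 95% at full capture and 52% at a quarter. The 5.0% zero-event bound is correct arithmetic for 58 fully questioned women. It shows what complete questioning would allow and should not be read as a measure of the defect. The absence of a harm question leaves the IRD comparison and its stated power unchanged.

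The conclusion rests on the visit lists being complete as written and on the consent form adding no scheduled question. The change should be made because it is inexpensive and puts both arms on the same footing, not because the documents show serious risk.

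**What to change.** 1. Reconcile the wear instruction in 10.1 with the effects in 14.1 and with both parts of 13.6, so that the take-home instruction says what is intended if a listed effect occurs during the session. The sponsor's clinicians decide the content. Check the consent form against the result.
2. State in 10.1 and 11.6 that a woman who removes the device early stays in follow-up and in the analysis in her randomised arm unless she withdraws consent.
3. At the next-day contact, Visit 2 and Visit 3, have blinded staff (not the technicians who program the boxes) ask one standard question covering the 14.1 list, in the same words for both arms, and record the answers with dates.
4. At box retrieval, record wear time and whether, when and why the device was removed early.
5. Add these items to 10.2, and add to 11.6 a descriptive table by arm of events, wear time and early removal. Complete 16.1 with how events are identified, who reports them, how often they are reviewed and the severity scale.

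Cost: revised instruction wording, a short item at three existing contacts and one extra table. There are no new visits and no change to the sample size or the IRD model. The downside is a few more minor events to record and report.
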